7. TRIAL DESIGN

Whilst a randomised-controlled trial (RCT) design is the gold standard for comparing interventions, current use of machine perfusion technologies mean that the majority of centres would not consider randomising certain groups of high-risk livers to static cold storage. Given this loss of equipoise, an RCT would be considered unethical and unlikely to successfully recruit. Despite this, the effect of NMP on utilisation and overall cost remains unknown and further evidence is required to determine if the technology should be routinely funded.

In order to determine the effect of routine availability of NMP on the utilisation of these livers, the current study will employ a "threshold-crossing" design as described by Eichler et al. (11). A real-world control cohort will be identified *a priori* from consecutive liver offers in the NHSBT transplant registry meeting trial inclusion criteria to determine functional utilisation where normothermic machine preservation was not routinely available. Using these data, a threshold will be set above which availability of NMP would be considered to have a significant clinical impact on utilisation. Once defined, a single-arm prospective trial will recruit participants with NMP routinely available, and analysis performed to see if the pre-defined threshold is crossed in the study cohort.

Definition of the control cohort and threshold in advance of recruitment minimises the risk of bias in selecting controls. Use of identical inclusion criteria in both study and control cohorts will ensure comparability of groups, which will also be confirmed in a secondary propensity-matched analysis.

Identification of eligible liver offers will be undertaken by the NHS Blood and Transplant (NHSBT) Hub Operations at the point of organ offer, before the recipient surgeon has any clinical information about the donor or liver being offered. This allows assessment of the impact of NMP on the whole of the transplant pathway including organ acceptance, assessment and subsequent transplantation.

All seven UK liver transplant centres will participate in the study. Upon identification of an eligible liver, the recipient centre will decide whether to take the NMP device to the donor hospital (device-to-donor), or to transport the liver under SCS and perfuse it on arrival at the implant centre (back-to-base). In either case, the implanting surgeon will make a decision whether to transplant based upon all available information (donor characteristics, organ appearance, histology and NMP parameters).

Liver offers that are declined by the initial centre will follow the existing NHSBT offering pathway. Inclusion in the study will be maintained when the liver is offered to subsequent transplant centres. If the accepting centre is unable to follow the study protocol because the intervention is not available, the liver will be excluded from modified intent-to-treat analysis.

Transplant recipients in the study cohort will be consented for use of their data and followed for 12 months post-transplant. Data collection timepoints will be pre-transplant, and at days 1-7, months 3 and 12 post-transplant. All study assessments and investigations are part of standard care other than quality of life questionnaires. Long-term patient and graft survival will be assessed using registry data at 5 years post-transplant.

Some eligibility criteria cannot be assessed until after recruitment, when the liver recipient and transplant type are known. In these cases (where patients are aged <18 years, have not agreed to use of NMP according to local consent policy, or do not consent to use of their data, or for split liver, multi-organ or non-UK transplants) the recipient will not be included in the study and the liver will be transplanted into

Clinical Trial Protocol Template version 14.0

the recipient as per standard care. If preservation has started prior to the consent process, the liver will continue to be preserved in the same manner until transplant. If preservation has not yet commenced, the liver will be preserved according to usual care in that centre.

Data will be collected into a secure central online electronic database using electronic case report forms.

Primary outcomes will be analysed 12 months following enrolment of the last liver offer to the study. Participant involvement in the study will complete at the last follow-up assessment of the last participant, 12 months post transplant, and the study will close. Collection of 5-year survival outcomes (beyond the end of the study) will be from the registry.

Anticipated flow of liver offers through the trial is depicted in *Appendix* 1.

8. STUDY COHORTS

8.1. Real world control (RWC) cohort

The real-world control cohort was defined in advance of recruitment of the prospective study cohort in order to minimise risk of bias in selection, and to allow the pre-defined efficacy threshold to be set.

All consecutive liver offers meeting the study inclusion and exclusion criteria defined in sections 8.3 and 8.4 between 1st January 2018 and 31st December 2019 were identified in the NHSBT transplant registry. This time period is contemporary enough to ensure stable utilisation over time, but excludes livers offered during the peaks of the coronavirus pandemic in the UK where offering and utilisation were affected by hospital capacity.

Broadly speaking, all livers with a donor utilisation index (DUI) greater than 0.27 from donors aged 16 years or over, offered to the seven participating UK liver transplant units, were eligible for inclusion. Those originating from or transplanted outside of the UK, or from Hepatitis C or HIV positive donors, were excluded. Livers that were split or reduced, that were transplanted as multi-organ transplants or where the recipient was aged <18 years were also excluded. Donor Utilisation Index was calculated using the formulae shown in Appendix 3, which differ for DBD and DCD donors. The DUI is a clinical risk score using eleven (DBD) or seventeen (DCD) donor demographic variables to predict graft utilisation. Recent analysis of UK donor data suggests that a cut-off of 0.27 represents the most poorly-utilised 60% of livers offered.

The RWC cohort included 2465 liver offers that met all these inclusion and exclusion criteria. Records maintained by the seven participating transplant centres allowed the identification of 118 livers from this cohort (5%) in which any form of *ex-vivo* machine preservation was used (including NMP and hypothermic machine preservation). These livers had lower DUI than the rest, and so excluding them would bias the cohort by excluding some lower risk livers. Instead, these livers remained in the control cohort, but their outcomes were imputed to match those of other livers that were retrieved for transplantation, which had a more similar risk profile. The remaining transplanted livers in the RWC cohort would therefore have been retrieved, preserved and transported according to NHSBT national protocols. This includes placement in ice-cold perfusion solution on the back-table, and subsequently stored in cold perfusion solution within an icebox. The organ will have been transported to the recipient centre and removed from storage prior to implantation for standard back-table preparation. The duration of cold storage will have been dictated by logistics and local policy.

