3. SYNOPSIS

Trial Title	Utilisation of normothermi livers - a national threshold-	c machine preservation in ex-	ktended criteria	
Internal ref. no. (or short title)	Perfused Liver Utilisation Study (PLUS)			
Trial registration	ISCRTN 11552402			
Sponsor	University of Oxford			
Funder	NIHR Invention for Innovation	on Challenge Awards (NIHR20)	1003)	
Clinical Phase	Phase III			
Trial Design	Threshold-crossing design w	rith a prospectively-defined eff	ficacy threshold.	
	Control cohort (static cold storage; SCS): A priori defined real-world control cohort meeting study inclusion criteria, identified from UK Transplant Registry held by NHS Blood and Transplant (referred to as 'the registry' throughout the protocol. Study cohort (normothermic machine perfusion; NMP): Prospectively identified, consecutive liver offers with a donor utilisation index (DUI) >			
	0.27 (appendix 3), in which	NMP is made available	. ,	
Trial Participants	Extended criteria (DUI > 0.27) liver offers made to participating centres through the NHSBT offering system			
Sample Size	Control cohort: 2465 (retrospective) Study cohort: 1035 liver offers (prospectively recruited in this study)			
Planned Trial Period	Total study: 01/10/2021 – 30/09/2026 (60 months) Participant follow-up: 12 months. Long-term patient and graft survival will be assessed using registry data at 5 years post-transplant			
Planned Recruitment period	11/04/2022 – 11/10/2023 (18 months)			
·	Objectives	Outcome Measures	Timepoint(s)	
Primary	To assess whether NMP can increase the availability of livers for transplantation without compromising outcome	Functional utilisation – transplantation of the liver with 12-month patient and graft survival	12 months post- transplant	
Secondary	To assess the cost-	Intervention costs	Pre-	
	effectiveness of NMP in the context of NHS	NHS Resource Use	transplant, Day 7,	
	commissioning guidelines	Quality of Life	Months 3 and 12	
	To assess biochemical liver function in the study	Biochemical liver function (ALT, GGT, INR, Bilirubin)	Days 1-7,	
	cohort	Daily serum lactate (whilst on ITU/HDU)	Month 12	
		Model for Early Allograft Function score (MEAF)		

	To compare graft and	Primary non-function	Day 7,
	patient survival between study and control cohorts.	Graft survival (death censored)	Months 3 and 12. Long-term (5 year).
		Graft survival (non- censored)	
		Patient Survival	
	To compare the use of	Length of ITU/HDU stay	Days 1-7,

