13.2. Description of Statistical Methods

Primary outcome reporting will occur after collection and analysis of data at 12 months following the enrolment of the last patient to the trial. The outcome measures are described in detail in section 6.

The study arm (NMP) will be compared against RWC cohort (SCS) defined in Section 8.1 at this point for all primary and secondary outcomes, except 5 year outcomes. 95% confidence intervals will be provided for all assessments of treatment effect. Baseline characteristics of the donors enrolled and transplanted will be presented separately, together with characteristics of the liver transplant recipients. A CONSORT diagram will show the flow of donor livers and recipients through the study, in particular the reasons for any post-enrolment exclusions which are necessary because study entry occurs before some exclusion criteria can be assessed.

The primary outcome is a binary outcome of functional utilisation at 12 months. As the 12-month visit may occur at a routine hospital appointment prior to 12 months, livers will be assumed to be functioning at 12 months if documented as functioning >10 months post-transplant. The primary outcome will be analysed using a logistic regression model to assess the effect of treatment on outcome, after adjustment for the important prognostic factors of donor type and use of normothermic regional perfusion (NRP). The odds ratio, 95% confidence interval and p-value for the treatment term in this logistic regression model will be the primary analysis for the trial. NMP will be concluded superior if the lower bound of the confidence interval exceeds the efficacy threshold which has been pre-specified at 40 extra livers transplanted with one-year function per year (an OR of 1.20).

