13.3. Sample Size Determination

There are 2465 livers in the retrospective control cohort. One-year functional utilisation in this group was calculated using complete organ utilisation data and a Kaplan-Meier estimate of transplant survival at one year, due to a small proportion of censored data prior to that point. One year functional utilisation in the control cohort was 21.8%. A 50% improvement in functional utilisation (to 32.7%) would represent an increase of around 135 extra transplants functioning at 1 year each year in the UK. This would transform waiting list mortality (50 patients in 2019-20) and average waiting times.

There will be some circumstances where, typically due to logistics (e.g. temporary NMP unavailability), centres will preserve a liver in the NMP study cohort using SCS. In the European Phase-3 trial, only one liver randomised to NMP crossed-over to the SCS arm (14). This figure is likely to be higher in the current study due to earlier study entry and logistical constraints, so we have allowed for a 15% crossover rate (25% due to logistical reasons, 5% eligibility message not relayed and 5% general cross-over). We will analyse the data on a modified ITT basis, whereby livers unable to be perfused for logistic reasons are excluded, along with those who were found to be ineligible after study entry.

Allowing for these exclusions and cross-over rate, the sample size was calculated based on an anticipated increase in the primary endpoint from 21.8% in the RWC cohort to 31.4% in the NMP mITT analysis. A 'superiority by a margin' design was used, such that with a 2.5% one-sided significance level the sample size will have 90% power to detect whether NMP is superior to SCS by the prespecified threshold (margin) of 40 extra livers transplanted with one year function per year. As there are 2465 livers in the control cohort, an allocation ratio of 3.5:1 was used to achieve the necessary power and this requires a sample size of 700 liver offers in the NMP study arm. As the primary endpoint uses mandatory data collected by NHSBT, loss to follow-up should be low. Allowing a 25% loss due to exclusions due to being unable to use NMP for logistical reasons and another 10% loss (due to withdrawal of consent, loss to follow-up and those meeting exclusion criteria after study entry), the number required increases to 1035 offers.

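### The control window is balanced across the seasons, the planned recruitment window is not, and the primary model has no season term: a low-severity gap that can be closed at almost no cost

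*Protocol*

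**What the plan says.** Section 8.1 of the protocol defines the controls as all consecutive eligible offers "between 1st January 2018 and 31st December 2019 were identified in the NHSBT transplant registry". It defends this period as recent enough for utilisation to be stable, and as avoiding the pandemic peaks, when "offering and utilisation were affected by hospital capacity". The Synopsis gives the planned recruitment period of the prospective cohort as "11/04/2022 – 11/10/2023 (18 months").

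Section 13.2 names one logistic regression as the primary analysis, with the treatment effect estimated "after adjustment for the important prognostic factors of donor type and use of normothermic regional perfusion (NRP"). Success requires the lower confidence bound to exceed the threshold of "40 extra livers transplanted with one-year function per year (an OR of 1.20"). Section 13.3 plans for a rise "from 21.8% in the RWC cohort to 31.4% in the NMP mITT analysis" and states that "with a 2.5% one-sided significance level the sample size will have 90% power".

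Section 13.4 adds a propensity-matched comparison as a secondary analysis. Its matching variables are not listed. The protocol does not mention season and gives no monthly or seasonal utilisation rates.

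**The concern.** The comparison is not randomised and its two arms come from different calendar windows. Identical inclusion criteria, on which section 7 relies for comparability, cannot equalise the mix of calendar months. Two full years weight every season equally. Eighteen months starting in April do not.

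If functional utilisation differs between the two halves of the year, part of that difference passes into the contrast between cohorts. This is separate from long-term drift between 2018-19 and 2022-23, which is what the stability argument in section 8.1 addresses. Unequal season mix would act even if annual utilisation were perfectly flat.

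The decision rests on a lower bound set against a margin of about 3.2 to 3.3 percentage points, so a shift of some tenths of a point matters when the result lies near the threshold. The covariates of the primary model are fixed in section 13.2 itself, so this is not a detail left to the statistical analysis plan.

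**Working it through.** **The plan's own figures.** With 1242 eligible offers a year (section 13.3), 40 livers are 40/1242 = 3.22 points. On a control rate of 21.8% that gives 25.02%, an odds ratio of 1.197. An odds ratio of exactly 1.20 gives 25.07%, a margin of 3.27 points. So the threshold reproduces.

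The size of the perfusion arm, for superiority by a margin m with 3.5 controls per study offer, is

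n = (1.960 + 1.282)² × [0.218×0.782/3.5 + 0.314×0.686] / (0.096 − m)².

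This gives 682 for m = 3.22 points and 692 for m = 3.27 points, against the stated 700. With 700 and 2465 offers the power on the log odds ratio scale is 91.0%. Losses: 700/0.75/0.90 = 1037, against 1035. These figures also reproduce.

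**Season mix, counted in days with both end dates included.**

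| | Control window | Planned recruitment | Difference |
|---|---|---|---|
| Total days | 730 | 549 | |
| 11 April to 10 October | 366 (50.1%) | 366 (66.7%) | +16.5 points |
| December to February | 180 (24.7%) | 90 (16.4%) | −8.3 points |

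**Carry-through.** Let d be the difference in functional utilisation between the April-October half and the other half, after whatever donor type and regional perfusion explain. If offers accrue evenly, the spurious difference between cohorts is

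bias = (0.667 − 0.501) × d = 0.165d, or about d/6.

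**Effect on the decision.** The documents give no value for d, so the values below are assumptions. At a true odds ratio of 1.20 the study arm stands at 25.07%, and the standard error of the log odds ratio is

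√[1/(2465×0.218×0.782) + 1/(700×0.2507×0.7493)] = 0.0999.

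The bias is added to 25.07% and the resulting log-odds shift is divided by 0.0999. For d = 4 points the arm moves to 25.73%, the log-odds shift is 0.0352, and the error is 1 − Φ(1.960 − 0.352) = 5.4%. For power, the bias is subtracted from 31.4%.

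| Assumed d (points) | Bias (points) | Livers a year (bias × 1242) | Share of the 3.27-point margin | One-sided error if the bias favours perfusion (nominal 2.5%) | Power if it runs the other way (91.0% without bias) |
|---|---|---|---|---|---|
| 0 | 0 | 0 | 0 | 2.5% | 91.0% |
| 2 | 0.33 | 4 | 10% | 3.7% | 88.0% |
| 4 | 0.67 | 8 | 20% | 5.4% | 84.2% |
| 6 | 1.00 | 12 | 31% | 7.6% | 79.7% |

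**How far the assumptions matter.** Two changes shrink these figures.

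- If only December to February differs from the rest of the year, the factor is 0.083, about one twelfth. Differences of 2, 4 or 6 points then give errors of 3.1%, 3.7% and 4.5%.
- If early accrual is slow, the first April-October period counts for less. As an illustration, take the go/no-go minimum of 200 offers (section 13.5) in the first six months and 835 spread evenly over the next twelve. The share of offers in the summer half is then 59.7%, the imbalance 9.5 points, and the errors about 3%, 4% and 5%.

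To produce the whole margin, d would have to be about 3.27 × 6 = 19.6 points, nearly the entire control rate.

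**The case against.** The strongest reply is that nothing in the protocol shows a seasonal pattern. A reader might take the remark on hospital capacity in section 8.1 as an admission that ordinary winters lower utilisation. It is not: that sentence concerns the pandemic peaks. The size, direction and existence of a seasonal difference are all assumed here. This stands.

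A reader might also infer that the whole of any seasonal difference enters the treatment effect. The documents do not support that. About one sixth enters under even accrual and about one twelfth if only December to February differs. Whatever acts through donor type or regional perfusion is adjusted for.

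Three further points have weight. The half-year used above begins and ends on the recruitment dates, so it shows the imbalance near its largest. The dates are planned dates and days are not offers: section 13.3 needs only 56% of eligible offers, so enrolment need not follow the calendar. The propensity-matched analysis may also take up some of the imbalance. However, it is secondary, and the protocol does not say that offer date or season is a matching variable.

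What these replies do not remove is the imbalance itself, which follows from the protocol's own dates, and a primary model whose listed covariates cannot correct for it.

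**Conclusion.** The point holds as a minor limitation. The planned windows differ in season mix by about 16.5 points, and the primary model as written has no term for it. Under even accrual and assumed half-year differences of 2 to 6 points, the bias is about 0.3 to 1.0 points. One-sided error at the threshold would then be about 3.7% to 7.6% in place of 2.5% if the bias favours perfusion, or power would fall to about 88% to 80% if it does not. If utilisation does not vary by season, nothing changes.

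It would be wrong to conclude that the design is biased towards perfusion, because the documents give no direction. It would also be wrong to conclude that a clear success could be due to season. Against the anticipated difference of 31.4% − 21.8% = 9.6 points, a bias of 1.0 point is about a tenth. The issue matters for a result close to an odds ratio of 1.20. No figure stated in the protocol is wrong. Severity is low, and the case for acting is that the remedy is nearly free.

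**What to change.** Before the analysis, pre-specify one of the following:

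- a season term in the logistic model of section 13.2, for example a sine/cosine pair on offer date; or
- if the primary model is to stay untouched, one sensitivity analysis with control offers weighted to the study cohort's actual calendar-month distribution. Actual months should be used rather than the planned dates, so that uneven accrual is handled.

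In either case, list calendar season among the variables of the propensity-matched analysis in section 13.4.

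The cost is a few lines of wording and one or two degrees of freedom among about 2465 + 700 = 3165 offers. No new data collection should be needed: both cohorts are consecutive registry offers and the controls were selected by date, so offer date should already be held for every liver.

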8.2. Study cohort

The study cohort will be prospectively recruited in a single-arm trial in the seven participating transplant centres. Inclusion and exclusion criteria will be identical to those used to define the RWC cohort, as defined in sections 8.3 and 8.4.

All eligible offers to the participating centres will be identified (by means of DUI calculation) by NHSBT Hub Operations, and eligibility for the study confirmed with the offer when made to the centres. All consecutive offers meeting the criteria will be included and outcomes analysed, other than where NMP is not available in the accepting centre for logistical reasons (eg. Lack of appropriate personnel or device availability) In these cases, the liver will be excluded from modified intent-to-treat analysis.

Clinical Trial Protocol Template version 14.0

CONFIDENTIAL

© Copyright: The University of Oxford and Oxford University Hospitals NHS Foundation Trust 2018

Full details of recruitment procedures are defined in section 9.

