Currently, around 1242 eligible livers (i.e. DUI>0.27 and Hep C/HIV negative) are offered each year on average in the UK. Recruitment would therefore require 56% of all eligible livers offered during the 18-month recruitment period to be enrolled in the trial.

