13.5. Embedded Feasibility Study

An embedded feasibility study will assess recruitment and the use of NMP in recruited livers, to ensure that NMP is used where feasible. Due to logistical constraints (absence of trained staff, device already in use etc.), NMP may not be available for use in all cases, but lack of use may reduce the ability of the study to demonstrate an improvement in utilisation.

Go/no-go points at the end of 6-months are as follows:

- Recruitment of a minimum of 200 liver offers
- NMP utilisation in transplanted livers of > 50%, as a measure of protocol compliance. This will be assessed at a centre level, and poorly performing centres may be withdrawn from the study.

If recruitment or compliance with the intervention are outside these targets, recruitment strategies will be reviewed and a decision made as to whether to proceed.

No further interim analyses are planned.

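### The study cohort is defined as every consecutive eligible offer, but the plan needs only 56% of them; the other 44% are unexplained, while the controls are all offers

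*Protocol*

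**What the plan says.** The synopsis describes the study cohort as prospectively identified, consecutive offers with DUI above 0.27. Section 8.2 is firmer: "All consecutive offers meeting the criteria will be included and outcomes analysed, other than where NMP is not available in the accepting centre for logistical" grounds. Section 8.1 builds the control cohort in the same way from the registry: "All consecutive liver offers meeting the study inclusion and exclusion criteria defined in sections 8.3 and 8.4 between 1st January 2018 and 31st December 2019". Its size is given in section 13.3: "There are 2465 livers in the retrospective control cohort".

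Section 13.3 counts the supply: "Currently, around 1242 eligible livers (i.e. DUI>0.27 and Hep C/HIV negative) are offered each year on average in the UK". After allowing for losses, "the number required increases to 1035 offers". The synopsis fixes recruitment at "11/04/2022 – 11/10/2023 (18 months"). Section 13.3 then concludes: "Recruitment would therefore require 56% of all eligible livers offered during the 18-month recruitment period to be enrolled in the trial".

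On success, section 13.2 requires the lower confidence bound for the treatment odds ratio to exceed 1.20, in a logistic model adjusted for donor type and NRP. Section 7 rests comparability on using the same inclusion criteria in both cohorts, with a secondary propensity-matched check.

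**The concern.** If all consecutive eligible offers enter, 18 months should yield about 1863 of them and the target should be met in about 10 months. The protocol sets 18 months and 1035 offers. It neither says that enrolment stops at 1035 nor gives a reason why an eligible offer would not be enrolled. The definition in section 8.2 and the recruitment arithmetic in section 13.3 therefore describe different cohorts.

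This matters because the trial has one non-randomised comparison. The controls are every eligible offer over two years. If the study cohort is a subset, identical criteria no longer guarantee comparable cohorts, and the result depends on which offers are missed. If missed offers are less usable than enrolled ones, part of the observed gain is selection. The primary model does not adjust for DUI, and the propensity match can work only on offers that were enrolled and on measured variables. The threshold is also a national yearly count (40 extra functioning livers), which a part-sample estimates only if it represents all offers.

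**Working it through.** **Inputs.** From section 13.3: 1242 eligible offers per year, 1035 to enrol, 700 to analyse, 2465 controls, control rate 21.8%, losses of 25% (logistical) and 10% (other). From the synopsis: 18 months. From section 13.2: threshold OR 1.20, judged on the lower confidence bound.

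**1. Reproduce the 56%.** 1242 × 1.5 = 1863; 1035 / 1863 = 55.6%. The control cohort's own rate gives the same answer: 2465 / 2 = 1232.5 per year; × 1.5 = 1849; 1035 / 1849 = 56.0%.

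**2. What consecutive enrolment would give.** Time to target: 1035 / 1242 × 12 = 10.0 months. Shortfall over 18 months: 1863 − 1035 = 828 offers.

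**3. Do the planned losses explain the gap?** 700 / (0.75 × 0.90) = 1037, against the stated 1035, so both losses are already inside the 1035. Section 8.4 does list logistical unavailability as an exclusion, which could be read as acting before entry. That reading does not close the gap either: the pool becomes 1863 × 0.75 = 1397, the number needed becomes 700 / 0.90 = 778, and 778 / 1397 is again 56%.

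**4. What counts as success.** OR 1.20 on 21.8%: odds 0.218 / 0.782 = 0.2788; × 1.20 = 0.3345; rate 25.1%. For an observed study rate p, unadjusted, SE(log OR) = √[1/(700·p·(1−p)) + 1/(2465 × 0.218 × 0.782)]. At p = 28.8%, OR = 1.45 and SE = 0.097; exp(ln 1.45 − 1.96 × 0.097) = 1.20. The success rule is therefore met from about 28.8% observed.

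**5. Selection with no NMP effect.** The documents give no data on unenrolled offers, so their rate u is an assumption. With enrolled rate e and 55.6% capture, 0.218 = 0.556e + 0.444u.

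| Result to be produced by selection alone | e | u | u/e | Share enrolled: functioning vs other offers |
|---|---|---|---|---|
| Point estimate OR 1.20 | 25.1% | 17.7% | 0.71 | 64% vs 53% |
| Lower bound above 1.20 | 28.8% | 13.1% | 0.45 | 73% vs 51% |

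**6. Selection with a true effect exactly at the threshold.** Let the rate over all eligible offers with NMP available be 25.07%, and let unenrolled offers run at r times the enrolled rate. Then e = 0.2507 / (0.556 + 0.444r), and the chance of declaring success is Φ[(ln OR − ln 1.20)/SE − 1.96], with nominal value 2.5%.

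| r (assumed) | e | OR | SE | Chance of false success |
|---|---|---|---|---|
| 1.00 | 25.1% | 1.20 | 0.100 | 2.5% |
| 0.90 | 26.2% | 1.28 | 0.099 | 9% |
| 0.80 | 27.5% | 1.36 | 0.098 | 25% |
| 0.75 | 28.2% | 1.41 | 0.097 | 38% |

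**The case against.** The protocol has real protections. Under section 9.2 the DUI tool runs automatically at each matching run, and under section 7 Hub Operations identifies eligible offers before the surgeon has any clinical information. Declined offers stay in the study, and livers refused by every centre count as discards (section 9.3). No passage lets a centre choose whether an offer is enrolled. These points stand and make strong selection less likely. They protect the comparison only if every identified offer is enrolled, which is what the 56% leaves open.

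Three stronger readings are tempting and not supported.

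- A reader might infer that the protocol plans to skip 44% of offers. Section 13.3 says only what share recruitment requires; it is a feasibility statement.
- A reader might infer that the six-month criterion, "Recruitment of a minimum of 200 liver offers", accepts 32% capture (200 of about 621). It is a feasibility floor that triggers review, and the 32% presumes that all centres were open for the whole six months, which the protocol does not say.
- A reader might infer that modest selection alone would meet the success rule. It would not. With no NMP effect and unenrolled offers at 75% of the enrolled rate, e = 0.218 / (0.556 + 0.444 × 0.75) = 24.5%, OR 1.17, lower bound 0.96.

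Replacing the primary cohort with every registry offer would also conflict with the consent requirements in sections 8.3, 9.5 and 13.4.

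**Conclusion.** The inconsistency is real and follows from the protocol's own figures: all consecutive offers in section 8.2, 56% of them in section 13.3, and up to about 828 eligible offers with no stated reason for non-enrolment, set against a control cohort that is complete. The planned losses do not account for it.

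Whether this biases the result cannot be known from the documents, and no selection mechanism is described. Under the assumptions shown (unadjusted analysis, 700 vs 2465, 56% capture), selection alone moves the point estimate to OR 1.20 if unenrolled offers function at about 17.7%. It meets the formal rule only at about 13%, less than half the enrolled rate. The more plausible harm is near the threshold: unenrolled offers at 90% to 75% of the enrolled rate would raise false success from 2.5% to roughly 9% to 38%. This calls for a clarification and a sensitivity analysis and does not show that the primary analysis is invalid.

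**What to change.** - **Sections 8.2 and 13.3.** Reconcile them: either enrol every identified offer until the target is met, or state why eligible offers would not be enrolled. If recruitment has already closed on the stated dates, only the second option remains.
- **Section 13.4.** Keep the mITT analysis as primary. Pre-specify a sensitivity analysis of functional utilisation over all registry offers with DUI above 0.27 that meet the liver-level criteria in the recruitment window, using anonymised registry data within the consent and information-governance limits.
- **Reporting.** Give the capture fraction, and the DUI, donor type and utilisation of enrolled versus unenrolled offers.

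The cost is one registry extract and a check on data permissions, because section 10.1 describes the anonymised route for the retrospective controls only. No new patients or procedures are needed. The NMP effect may be diluted in the sensitivity analysis, since it would include offers for which NMP was not in play; the report should say so.
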